y. In the combination therapy arm, pembrolizumab will be administered as an intravenous infusion over 30 min followed by ASP0739 administration at least 1 hour after pembrolizumab administration. For participants enrolled in Japanese safety lead-in, C1D8 assessments should be performed prior to discharge from hospital.

z. If participant is completing all assessments within cycle 6, EOT assessment will be on C6D22 (± 3 days) or prior to the initiation of new anticancer therapy, whichever occurs first.

aa. Only participants in the combination therapy arm need to undergo pulmonary function tests at screening and at weeks 12 and 24 (before dose 3 and dose 5 of pembrolizumab, respectively) of study treatment.

bb. These assessments only apply to the Japanese participants.

Footnotes continued on next page

Table 3 Schedule of Assessments for Follow-up Periods

Visit	Safety Follow-up			Follow-up Period Year 1^a	Survival Follow-up
	30 day ^b	60 day ^b	90 day ^b		
Window (days)	± 3	± 3	± 3	Every 8 weeks ^c	Every 3 months
Physical Examination	X	X	X		
Vital Signs	X	X	X		
ECOG Performance	X	X	X		
Concomitant Medications	X	X	X		
12-Lead ECG	X	X	X		
Clinical Laboratory Tests (chemistry, hematology, coagulation, urinalysis)	X	X	X		
Pregnancy Test for WOCBP	X	X	X		
AE/SAE Assessment	X	X	X		
Pharmacokinetic sample for cell kinetics (ASP0739)	See Table 5 for sample time points				
Blood Sample for NY-ESO-1 antibody	X	X	X	X ^d	
Blood Sample for Immune Response Biomarker (ELISpot)	X	X	X	X ^e	
Blood Sample for Immune Response Biomarker (Tetramer)	X	X	X	X ^d	
Blood Sample for Immune Cell Phenotyping	X	X	X	X ^e	
Blood Sample for Cytokines	X	X	X	X ^e	
Blood Sample for ctDNA	X	X	X	X ^f	
Radiographic Disease Assessment	Every 56 ± 7 days				
Survival Follow-up ^g					X

AE: adverse event; ctDNA: circulating tumor DNA; ECG: electrocardiogram; ECOG: eastern cooperative oncology group; ELISpot: enzyme-linked immunospot; EOT: end of treatment; NY-ESO-1: New York esophageal squamous cell carcinoma 1; SAE: serious adverse event; WOCBP: woman of childbearing potential

a. Follow-up visits every 2 months or until progression or start of a new anticancer therapy or death (whichever occurs first).

b. From the last dose.

Footnotes continued on next page

- c. From EOT or the last planned assessment if EOT was not performed.
- d. Maximum of 5 samples collected during Follow-up Period Year 1. Samples will be collected at the time of the disease assessment visit.

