4 STUDY DESIGN AND DOSE RATIONALE

4.1 Overall Study Design

This is a phase 1, open-label study of ASP0739 in participants with R/R solid tumors known to express NY-ESO-1 and a phase 2 study of single agent and combination therapy with pembrolizumab in participants with R/R SS, MRCL or ovarian cancer.

Phase 1 (dose escalation) in participants with solid tumors known to express NY-ESO-1 and phase 2 of ASP0739 single agent and combination therapy with pembrolizumab in R/R SS, MRCL and ovarian cancer who have not responded to SOC or are ineligible for standard therapy. Phase 2 single agent will also include a cohort of participants with select solid

tumors known to express NY-ESO-1 (melanoma, NSCLC-adenocarcinoma and squamous cell and ESCC).

Both study phases consist of the following periods:

- Screening (up to 28 days)
- Treatment with ASP0739 (up to 6 doses every 28 days) and for participants in combination cohorts with pembrolizumab on cycle 1 day 1 (C1D1), and then every 6 weeks, until disease progression, unacceptable toxicity or up to 17 doses
- EOT visit after completion of IP: Within 7 days of EOT determination or prior to the initiation of new anticancer therapy, whichever occurs first
- Safety follow-up visits at 30, 60 and 90 days from the last dose of treatment or prior to the initiation of new anticancer therapy
- Follow-up visits every 2 months for up to 1 year or until progression or start of a new anticancer therapy or death (whichever occurs first)
- Survival follow-up for up to 1 year by telephone calls every 3 months after the start of a new anticancer treatment or progression after ASP0739 and/or pembrolizumab treatment

ASP0739 Single Agent

Participants will receive an intravenous infusion of ASP0739 (HEK293 transfected with a lentiviral vector that is encoding the target antigen NY-ESO-1). Participants will receive 1 dose every 28-day cycle for up to 4 doses; an additional 2 doses may be administered in participants with a partial response (PR) or stable disease (SD). Following the first 2 cycles, participants who have not met any individual treatment discontinuation criteria and are receiving clinical benefit may continue further treatment with ASP0739, as decided by the investigator.

ASP0739 Combination with Pembrolizumab

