7.3 Adverse Events and Other Safety Aspects

The definitions of an AE or SAE can be found in [Sections [10.3.1](#) and [10.3.2](#)], respectively. AEs will be reported by the participant (or, when appropriate, by a caregiver, surrogate, or the participant's legally authorized representative).

The investigator and any qualified designees are responsible for detecting, documenting and recording events that meet the definition of an AE or SAE and remain responsible for following up AEs that are serious, considered related to the study IP and other procedures, or that caused the participant to discontinue the IP and other procedures and/or study [see Section [10.3](#) Appendix 3: Adverse Events: Definitions and Procedures for Recording, Evaluating, Follow-up and Reporting].

The method of recording, evaluating, and assessing causality of AE and SAE and the procedures for completing and transmitting SAE reports are provided in [Section [10.3](#) Appendix 3: Adverse Events: Definitions and Procedures for Recording, Evaluating, Follow-up and Reporting].

7.3.1 Time Period and Frequency for Collecting Adverse Event and Serious Adverse Event Information

All SAEs will be collected from the signing of the ICF until the follow-up visit at the time points specified in the schedule of assessments [[Table 1](#) through [Table 3](#)] and reported on the eCRF.

All AEs will be collected from the signing of the ICF until the follow-up visit at the time points specified in the schedule of assessments [[Table 1](#) through [Table 3](#)] and reported on the eCRF.

If the NCI-CTCAE grade/grade of an SAE/AE changes, the event should be relisted on the eCRF with the new NCI-CTCAE grade/grade and new onset date.

If the NCI-CTCAE grade/grade of an SAE/AE decreases, the SAE/AE should be relisted on the eCRF with the new NCI-CTCAE grade/grade and new onset date. The exception is ongoing pre-dose events that continue post-dose and improve post-dose. Such events should not be re-listed.

If the NCI-CTCAE grade/grade of an SAE reduces, the details of the AE should be provided on the SAE worksheet for the medical assessor to be able to assess the course of the event.

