### **5.2.3 Safety Endpoint: Adverse Events (AEs)**

An AE is any untoward medical occurrence in a participant or clinical study participant, temporally associated with the use of study IP and other study treatments, whether or not considered related to the study IP and other study treatments.

A treatment-emergent adverse event (TEAE) is defined as an AE observed after starting administration of the IP until 30 days after the final administration of IP. An IP-related TEAE is defined as any TEAE with a causal relationship assessed as “yes” by the investigator or with missing assessment of the causal relationship.

If the adverse event occurs on Day 1 and the onset check box is marked “Onset after first dose of study IP” or the onset check box is left blank, then the adverse event will be considered treatment emergent. If the adverse event occurs on Day 1 and the onset check box is marked “Onset before first dose of study IP”, then the adverse event will not be considered treatment emergent. If a participant experiences an event both during the pre-investigational period and during the investigational period, the event will be considered as TEAE only if it has worsened in severity (i.e. it is reported with a new start date). All adverse events

collected that begin within 30 days after taking the last dose of study IP will also be counted as TEAE.

The number and percentage of participants with TEAEs, IP-related TEAEs, serious TEAEs, IP-related serious TEASs, TEAEs leading to withdrawal of treatment and IP-related TEAEs leading to withdrawal of treatment will be summarized by SOC, preferred term and treatment group. The number and percentage of TEAEs by severity will also be summarized. The worst severity will be summarized if the same AE is recorded more than once for a participant.

AE data will be listed.

Immune-related AE (irAE) and infusion related reactions (IRR) will be considered as Adverse Events of Special Interest (AEsi). The list of events classified as AEsi may change during the study due to ongoing pharmacovigilance.

Time to first onset of irAE will follow the following algorithm:

Situation	Date of Event or Censor	Outcome
AE of interest observed	Date of first onset	Event
No AE of interest observed and treatment ongoing	Date of data cutoff	Censor
No AE of interest observed and treatment discontinued	Date of last dose + 30 days	Censor

Time to First Onset = Date of Event or Censor – Date of First Dose +1

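### Time to first irAE uses two windows: events have no onset limit, but event-free participants off treatment are censored at last dose + 30 days, with no cap at death, last contact or cutoff

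*SAP*

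**What the plan says.** SAP 5.2.3 makes irAEs adverse events of special interest and sets out an algorithm for time to first onset, with three rows:

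- Event: "AE of interest observed", dated "Date of first onset". The row gives no latest onset date and does not restrict events to treatment-emergent ones.
- Censored at data cutoff: "No AE of interest observed and treatment ongoing".
- No event and treatment discontinued: censored at "Date of last dose + 30 days".

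The same section defines a treatment-emergent AE as one "observed after starting administration of the IP until 30 days after the final administration of IP", but the algorithm does not refer to that definition.

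Collection runs longer than 30 days. Protocol 7.3.1 states: "All AEs will be collected from the signing of the ICF until the follow-up visit". Protocol 4.1 plans "Safety follow-up visits at 30, 60 and 90 days from the last dose of treatment" (or before new anticancer therapy), and the row "AE/SAE Assessment" in Protocol Table 3 is marked at all three visits. SAP 6.5.2 summarizes AEs to 30 days after last treatment, but serious AEs to 90 days. SAP 6.5.3 plans only the number and percentage of participants with AEs of special interest.

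**The concern.** Censoring should depend only on how long a participant was watched, not on whether the event occurs later. Here it depends on the outcome. Two participants with the same last dose are both seen at 30, 60 and 90 days. If one has a first irAE on post-dose day 60, that participant stays at risk to day 60. The other, equally observed and event-free, is removed at day 30. Beyond last dose + 30, a participant who has stopped treatment remains in the risk set only because an event is coming. A Kaplan-Meier curve or an exposure-adjusted rate built from these dates would be too high, and in a small trial one late event could dominate it.

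A second fault lies in the same row. Last dose + 30 is applied even if the participant died, was lost or reached data cutoff before that day, so event-free time is credited when nobody was observing.

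**Working it through.** The plan states no rate, power or sample size for this endpoint, so there is no figure to reproduce. The check concerns the direction and possible size of the bias.

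**Inputs from the documents.** Event and censoring rules: SAP 5.2.3. AE collection to 90 days: Protocol 4.1, 7.3.1 and Table 3. Dosing every 28 days for 4 doses: Protocol 4.1, so the last dose falls on day 1 + 3 × 28 = 85. Illustrative N = 12: the upper end of the planned dose-escalation size in Protocol 4.1.

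**Worked example.** Twelve participants have their last dose on day 85. One has a first irAE 60 days later (day 145) and no one else has one. With S = ∏(1 − d/n), where d is the number of events and n the number at risk:

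- As written: 11 participants are censored on day 85 + 30 = 115. On day 145, n = 1 and d = 1, so 1 − S = 1 − (1 − 1/1) = 100%.
- 90 days for both rows: 11 are censored on day 85 + 90 = 175. On day 145, n = 12 and d = 1, so 1 − S = 1/12 = 8.3%.
- 30 days for both rows: day 145 lies beyond day 115, so there is no event and 1 − S = 0%.
- Crude proportion: 1/12 = 8.3% (0/12 if only treatment-emergent events count). The censoring date plays no part.

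**Range under assumed rates.** The documents give neither irAE rates nor an exposure distribution, so these are assumptions. First set: constant irAE hazard; last dose independent of irAE risk; 40%, 35% and 25% of participants receiving 2, 4 and 6 doses (last dose on day 29, 85 or 141); N = 12. Estimated incidence at day 171 (141 + 30):

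| True | As written | 30 days, both rows | 90 days, both rows |
|---|---|---|---|
| 10% | 16.2% | 10.2% | 10.2% |
| 20% | 30.6% | 19.9% | 19.9% |
| 30% | 42.8% | 29.2% | 29.7% |

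The excess over the true value is 6.2, 10.6 and 12.8 percentage points. At N = 43 and N = 181 the as-written estimates are within 2 points of these, so this is bias and not small-sample noise. Either consistent rule removes it.

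Second set: last dose at cycle 1, 2, 3 or 4 in 10%, 50%, 10% and 30%, and a hazard of −ln(0.9)/90 per day up to last dose + 30. A consistent 30-day rule then gives 10.0% at day 90 and 1 − 0.9^(115/90) = 12.6% at day 115. As written:

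| Hazard after last dose + 30 | Day 90 | Day 115 |
|---|---|---|
| Unchanged | 14.8% | 21.5% |
| Halved | 12.5% | 17.4% |
| One tenth | 10.6% | 13.6% |
| Zero | 10.0% | 12.6% |

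With the unchanged hazard but the first set's exposure split, the as-written figures are 11.9% and 16.0%. The direction is stable; the size is not, and it vanishes when there are no late irAEs.

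**The uncapped date.** A participant who dies 10 days after the last dose is censored at day 30 and gains 30 − 10 = 20 days of event-free time that never existed. The same holds for a data cutoff or last contact on that day. This enlarges the risk set and biases an estimate downward.

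**The case against.** The strongest reply is that no affected estimate is planned. SAP 6.5.3 asks only for a number and percentage, and no Kaplan-Meier or cumulative-incidence method is named for irAEs. Even OS, PFS and duration of response are only listed (SAP 6.4.2.4 to 6.4.2.8). That stands. A reader might infer that the trial's reported irAE incidence will be inflated; the documents do not support that, because a crude proportion does not use the censoring date.

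The second reply is that treatment-emergent was surely meant: last dose + 30 is exactly the end of the treatment-emergent window in the same section. That is the likely intent, and under it the two rows agree. But the table does not say so, and SAP 6.5.2 carries serious AEs to 90 days, so a serious irAE on day 60 remains ambiguous.

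Third, a reader might infer that late irAEs are expected here. Protocol 10.10 does say irAEs can appear months after the last dose, but of pembrolizumab, and SAP 1 records that no combination treatment was given. For ASP0739 the protocol expects irAEs from its mechanism without saying they occur late.

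Finally, the risk set beyond day 30 consists only of future events within a group sharing the same last-dose day. A pooled risk set also holds participants still on treatment, which is why the simulated bias is far smaller than in the worked example.

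**Conclusion.** The point holds as a defect in a stated rule, at minor severity. The event and censoring rows of SAP 5.2.3 use different windows, and a table of event dates, censoring dates and outcomes serves only time-to-event use. Any such estimate would be biased upward by first irAEs on post-dose days 31 to 90, and downward by the uncapped censoring date; the documents do not allow the two to be netted. The worked example (100% against 8.3% or 0%) shows the mechanism and is not a forecast. The simulated excess runs from nil to about 13 points at the time points examined, and rests on assumed irAE rates, exposure and late hazard. The planned number and percentage is unaffected by the censoring date, though its numerator still needs a stated onset window.

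**What to change.** Use one window for both rows of the SAP 5.2.3 table. The simplest form counts only treatment-emergent irAEs (onset on or before last dose + 30 days). It censors event-free participants off treatment at the earliest of last dose + 30 days, death, last contact or data cutoff, and lists later irAEs separately. Using 90 days in both rows with the same caps is equally consistent and keeps the late events in the analysis. If an estimate is intended, name the estimator; if only a listing is intended, say so.

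The cost is two lines in one table. It needs no new data and no change to visits or collection.

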#### **5.2.4 Safety Endpoint: Laboratory Assessments**

For quantitative clinical laboratory measurements (hematology and biochemistry), descriptive statistics will be used to summarize results and change from baseline by dose level and overall and by time point. Shifts from baseline to the worst grade based on NCI-CTCAE v5.0 in laboratory tests will also be tabulated.

Laboratory data will be listed.

Clinical laboratory variables for hematology, chemistry including liver function test, coagulation, urinalysis, and bone marrow will be collected during the conduct of the study as listed in [Table 6](#) below.

Additional laboratory tests should be performed according to institutional standard of care.

**Table 6 Clinical Laboratory Tests**

Panel/Assessments	Parameters to be Analyzed	NCI-CTCAE Grading (Hyper/Hypo)
CBC with Differential	Hematocrit (Hct) Hemoglobin (Hgb) Platelet count Red blood cell count (RBC) White blood cell count (WBC) White blood cell count differential Absolute neutrophil count Absolute lymphocyte count	NA Both Hypo NA Both NA Hypo Both
Biochemistry	Sodium (Na) Potassium (K) Chloride (Cl) Bicarbonate (HCO3) Blood urea nitrogen (BUN) Creatinine (Cr) Glucose (Gl) Calcium (Ca) Phosphorus Magnesium (Mg) Albumin (Alb) Total protein (T Prot) Alkaline phosphatase (ALP) Lactate dehydrogenase (LDH) Creatine phosphokinase (CPK) Liver function tests including*: Bilirubin total (TBL) Alanine aminotransferase (ALT) Aspartate aminotransferase (AST)	Both Both NA NA NA Hyper Both Both NA Hypo NA Hyper NA Hyper Hyper Hyper Hyper
Table continued on next page		

Panel/Assessments	Parameters to be Analyzed	NCI-CTCAE Grading (Hyper/Hypo)
Urinalysis	Color Appearance Specific gravity pH Bilirubin Blood Glucose Ketones Leukocyte esterase Nitrite Protein Urobilinogen	NA NA NA NA NA NA NA NA NA NA NA NA
Urine/Serum Pregnancy Test *	hCG (Positive/Negative)	NA
Coagulation Profile (PT/INR, D-Dimer, Fibrinogen)	Activated partial thromboplastin time (aPTT) International normalized ratio (INR) Prothrombin time (sec) (PT) Fibrinogen D-Dimer	Hyper Hyper NA NA NA

eCRF: electronic case report form; hCG: human chorionic gonadotrophin

\* Local results will be collected and entered into the eCRF.

### **5.2.5 Safety Endpoint: Vital Signs**

Vital signs will include:

- Systolic and diastolic blood pressures (mmHg)
- Pulse rate (beats/minute)
- Respiratory rate (breaths/minute)
- Body temperature (degrees C)
- Height (m) (Height measurement performed at screening only) and weight (kg)

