- t. In both the monotherapy and combination cohorts, each participant must remain at the site facility for 4 hours following the participant's first dose of ASP0739. For the next dose (second dose) or additional subsequent single agent with ASP0739, participants must remain at the site facility for at least 2 hours after ASP0739 dosing.
- u. In the combination therapy arm, pembrolizumab will be administered as an intravenous infusion over 30 min followed by ASP0739 administration at least 1 hour after pembrolizumab administration. For participants enrolled in Japanese safety lead-in, C1D8 assessments should be performed prior to discharge from hospital.
- v. Samples collected at pembrolizumab doses 5, 7, 9, 11 and 13 only.
- w. Samples collected at pembrolizumab doses 5 and 7 only.
- x. Sample collected at the time of discontinuation due to disease progression.
- y. If participant is completing all assessments within cycle 6, EOT assessment will be on C6D22 (± 3 days) or prior to the initiation of new anticancer therapy, whichever occurs first.
- z. Only participants in the combination therapy arm need to undergo pulmonary function tests at screening and at weeks 12 and 24 of study treatment.

Table 2 Schedule of Assessments for Dose Expansion Monotherapy and Combination Therapy Cohort

	Scr	Treatment ^a																Pembrolizumab Monotherapy	EOT^{u,aa}
		Cycle 1						Cycle 2						Cycles 3–4 ^b		Cycles 5–6 ^c		Doses 5–17 ^d	
Visit Days	(-28 to -1)	1	2	4	8	15	22	1	2	4	8	15	22	1	15	1	15	Every 6 weeks	
Window(days)		0	0	± 1	± 1	± 1	± 1	± 1	0	± 1	± 1	± 1	± 1	± 3	± 1	± 3	± 1	± 3	+ 7
Signed ICF	X																		
Medical and Disease History	X																		
Physical Examination ^e	X ^e	X ^e	X	X ^{bb}	X	X	X	X ^e	X	X ^{bb}	X	X	X	X ^e	X	X ^e	X	X ^e	
Vital Signs ^f	X	X	X	X ^{bb}	X	X	X	X	X	X ^{bb}	X	X	X	X	X	X	X	X	
ECOG Performance	X	X ^g	X		X	X	X	X ^g	X		X	X ^h	X	X ^{g,h}	X ^h	X ^{g,h}	X ^h	X ^{g,h}	X
MUGA or ECHO	X ⁱ																		
12-Lead ECG ^j	X	X ⁱ						X ^j						X ^j		X ⁱ			X
Prior and Concomitant Medications	X ^k	X	X	X ^{bb}	X	X	X	X	X	X ^{bb}	X	X	X	X	X	X	X	X	X
Pregnancy Test for WOCBP	X	X ^l						X ^l						X ^l		X ^l		X ^l	X
Clinical Laboratory Tests (chemistry, hematology, urinalysis) ^m	X	X ^g	X		X	X	X	X ^g	X		X	X ^h	X	X ^{g,h}	X ^h	X ^{g,h}	X ^h	X ^{g,h}	X
Coagulation Profile (PT/INR, fibrinogen) ^m	X	X ^g	X		X	X	X	X ^g	X		X	X ^h	X	X ^{g,h}	X ^h	X ^{g,h}	X ^h	X ^{g,h}	X

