7.2.2 Vital Signs

- Oral temperature, pulse rate, respiratory rate, and blood pressure will be assessed as specified in the schedules of assessments [[Table 1](#) through [Table 3](#)].
- Blood pressure and pulse measurements will be assessed with a completely automated device. Manual techniques will be used only if an automated device is not available.
- Blood pressure and pulse measurements should be preceded by at least 5 min of rest for the participant in a quiet setting without distractions (e.g., television, cell phones).
- Vital signs will be measured in a semi-supine position after 5 min of rest and will include temperature, systolic and diastolic blood pressure and pulse.

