#### **6.5.5 Vital Signs**

The baseline value is the last measurement taken prior to the first IP administration.

Vital signs (systolic blood pressure [SBP], diastolic blood pressure [DBP], pulse, body temperature and weight) will be summarized using mean, standard deviation, minimum, maximum and median by dose level, phase, and overall. Additionally, a within-participant change will be calculated per visit as the post-baseline measurement minus the baseline measurement and summarized by visit.

Tables for potentially clinically significant vital signs will be generated using baseline value and highest post-baseline value for each participant.

The following criteria are defined as clinically significant for each parameter:

Vital Sign Variable	Criteria
SBP	$\geq 180$ mmHg AND $\geq 20$ mmHg change from baseline
DBP	$\geq 105$ mmHg AND $\geq 15$ mmHg change from baseline
Pulse Rate	$\geq 120$ bpm AND $\geq 15$ bpm change from baseline

Vital signs data will be displayed in listings.

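### SAP 6.5.5 leaves respiratory rate out of the vital-sign summaries, although SAP 5.2.5 names it as a safety endpoint and protocol 9.4.3.3 excludes no vital sign

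*SAP*

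**What the plan says.** SAP section 5.2.5 defines the vital-sign safety endpoint and lists "Respiratory rate (breaths/minute" next to blood pressure, pulse rate, temperature, height and weight. SAP section 5.2 counts vital signs among the measures of safety and tolerability, which are primary endpoints.

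SAP section 6.5.5 gives the analysis: "Vital signs (systolic blood pressure [SBP], diastolic blood pressure [DBP], pulse, body temperature and weight) will be summarized". The parenthesis is a closed list without respiratory rate. Changes from baseline are calculated and summarized per visit for the same signs. The section adds tables of extreme values ("Tables for potentially clinically significant vital signs will be generated using baseline value and highest post-baseline value for each participant"), with criteria for systolic pressure, diastolic pressure and pulse rate only. It ends with "Vital signs data will be displayed in listings".

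Protocol section 9.4.3.3 plans summaries of vital-sign results and of changes from baseline, by dose level and time point, with no sign excepted.

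Protocol section 7.2.2 is not consistent on what counts as a vital sign. Its first bullet reads "Oral temperature, pulse rate, respiratory rate, and blood pressure will be assessed as specified in the schedules of assessments". Its last bullet says vital signs are measured semi-supine "and will include temperature, systolic and diastolic blood pressure and pulse", with respiratory rate absent.

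**The concern.** If the SAP is followed as written, one repeatedly measured component of the primary safety endpoint gets no summary, although the protocol plans summaries of vital signs without exception. The SAP does not say that this is intended.

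The sign has some relevance here. ASP0739 is given intravenously, infusion-related reactions are adverse events of special interest in SAP section 5.2.3, and protocol section 2.3.1.1 names shortness of breath and wheeze among the signs of infusion reaction or anaphylaxis. Other scheduled measurements of breathing do not reach the participants who were treated. On pulmonary function, Table 1 footnote z says: "Only participants in the combination therapy arm need to undergo pulmonary function tests". SAP section 1 states that no combination treatment was given. What is at stake is a descriptive safety table: a change in respiratory rate around dosing could be found only by reading individual listings.

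**Working it through.** No power or error-rate calculation bears on this point. The check compares parameter lists and then counts the readings affected.

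**1. SAP 5.2.5 against SAP 6.5.5**

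| Sign in SAP 5.2.5 | Summarized in SAP 6.5.5 | Summarized elsewhere |
|---|---|---|
| Systolic pressure | yes | – |
| Diastolic pressure | yes | – |
| Pulse rate | yes | – |
| Body temperature | yes | – |
| Weight | yes | also at baseline, SAP 6.2.3 |
| Height | no | yes, at baseline, SAP 6.2.3 (measured at screening only) |
| Respiratory rate | no | no |

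Seven items are defined and five are summarized. Of the other two, height is measured once and covered at baseline. Respiratory rate is the only vital sign measured repeatedly that has no summary.

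**2. Is the omission explained?** SAP section 1 says that, after early termination, the plan covers part of the protocol analysis according to the data available. Note (3) in SAP section 2.1 then names the safety data that will be absent: serum, coagulation and physical examination. Vital signs are not named, and SAP 5.2.5 keeps respiratory rate. Nothing in the SAP accounts for the gap.

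**3. Is another breathing measurement scheduled for single-agent participants?**
- Pulmonary function tests: combination arm only (Table 1 footnote z, Table 2 footnote aa).
- Pulse oximetry: only in the additional exclusion criteria for combination cohorts (protocol section 5.2).
- Physical examination: data will not exist (SAP 2.1, note 3).

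Respiratory rate is the only one left.

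**4. Readings affected.** For ASP0739-only dosing days, Table 1 footnote g and Table 2 footnote f require vital signs before the infusion, at its end, and 30 minutes, 1 hour and 2 hours afterwards: 5 readings. Readings at 3 and 4 hours are optional. Readings every 15 minutes during the infusion are also specified. Protocol section 6.1.1 gives about 50 mL at 4 to 6 mL/min:
- 50 / 6 = 8.3 min
- 50 / 4 = 12.5 min

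The infusion therefore ends before the nominal 15-minute reading. The 5-minute early window could still allow one in a slow infusion, so 5 is a minimum for the day. Protocol section 4.1 allows up to 6 doses:
- 1 dose: 5 × 1 = 5
- 6 doses: 5 × 6 = 30

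The range is 5 to 30 required dosing-day readings per participant, with non-dosing visits in addition.

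**5. Would adding the parameter alone show a shift around dosing?** No. SAP 6.5.5 calculates and summarizes change by visit and mentions no time point. SAP section 6.5.6, on electrocardiograms, specifies both visit and time point. Protocol 9.4.3.3 says time point for vital signs. The list and the level of summary both need changing.

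**The case against.** The case for leaving SAP 6.5.5 alone has several parts.

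- **Respiratory rate is still reported.** A reader might infer that it disappears from the report. It does not, because SAP 6.5.5 lists vital-sign data. This stands: the gap is in summaries only.
- **Breathing problems still reach tables.** A reader might infer that respiratory harm would go unseen. Protocol section 10.3.1.1 has clinically significant vital-sign abnormalities reported as adverse events, SAP section 6.5.2 tabulates those events, and SAP section 6.5.3 summarizes infusion reactions and immune-related events separately. This stands and sets the low weight of the point.
- **The nonclinical emboli do not help.** Table 6 of the protocol mentions emboli, and a reader might take that as a lung signal. They are reported under liver and spleen. They give no support here.
- **The count can be overstated.** A figure of 20 to 30 readings assumes 4 to 6 doses. Continuation after cycle 2 depends on clinical benefit, so early stoppers have 5 or 10 dosing-day readings.
- **The numbers are small.** Protocol section 2.3.1.1 reports 4 participants dosed by 06 May 2022, and escalation planned about 12. The final number is not given. Listings of that size are readable, and the SAP already only lists survival and duration endpoints. This lowers the value of a summary, but SAP 6.5.5 summarizes the other repeated vital signs in the same participants.
- **The protocol is ambiguous.** SAP 6.5.5 equals the last bullet of protocol 7.2.2 plus weight, so it may simply follow that bullet. That may well be how the omission arose. It does not justify it, because SAP 5.2.5 follows the first bullet.

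**Conclusion.** The point holds as a minor correction. SAP 5.2.5 and SAP 6.5.5 disagree on respiratory rate, SAP 6.5.5 is narrower than protocol 9.4.3.3, and no reason is stated. The effect is limited to one descriptive safety table: 5 to 30 required dosing-day readings per participant, plus non-dosing visits, would be listed but not summarized. Efficacy, error rates and sample size are not affected, and the documents do not support a claim that a respiratory safety signal would be lost.

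This rests on three assumptions: that respiratory rate was collected as the first bullet of protocol 7.2.2 and SAP 5.2.5 say; that the regular schedules in Tables 1 and 2 applied rather than the crisis schedules of Appendix 12; and that the time point in protocol 9.4.3.3 means the reading within a visit, as it does in the electrocardiogram section of the SAP.

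**What to change.** 1. In SAP 6.5.5, change the list to: SBP, DBP, pulse, respiratory rate, body temperature and weight.
2. In the same section, summarize values and changes from baseline by visit and by time point, in line with protocol 9.4.3.3, so that change from before to after infusion can be seen.
3. State in the SAP or the clinical study report that the two bullets of protocol 7.2.2 disagree and that the first, which includes respiratory rate, was applied. A protocol amendment is not needed: the study has ended early, and an amendment could not change data already collected.

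No threshold for the extreme-value table is proposed.

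The cost is one more parameter in an existing table program, a time-point level in its layout, and a sentence of text. No new procedure or data collection is involved.
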